## CoVPN 5002

### SARS-COV-2 PREVALENCE STUDY

#### LIST OF ABBREVIATIONS AND ACRONYMS

Ab(s)	Antibody/Antibodies
ACTG	AIDS Clinical Trials Group
ADA	Antidrug antibodies
AE(s)	Adverse Event(s)
ARDS	Acute Respiratory Distress Syndrome
CDC	(United States) Center for Disease Control and Prevention
CFR	Code of Federal Regulations
COVID-19	Coronavirus Disease 2019
CoVPN	COVID-19 Prevention Network
CRMS	(NIAID) Clinical Research Management System
CRPMC	(NIAID) Clinical Research Products Management Center
CRF(s)	Case Report Form(s)
DAIDS	Division of AIDS
DHHS	US Department of Health and Human Services
EUA	Emergency Use Authorization
FDA	(United States) Food and Drug Administration
HPTN	HIV Prevention Trials Network
HVTN	HIV Vaccine Trials Network
ICF(s)	Informed consent form(s)
ICH	International Council for Harmonisation
IDCRC	Infectious Diseases Clinical Research Consortium
IMPAACT	International Maternal Pediatric Adolescent AIDS Clinical Trials Group
IoR	Investigator of Record
IRB(s)	Institutional Review Board(s)
LAR	Legally Authorized Representative
LC	Laboratory Center
LOC	Leadership and Operations Center
mAb(s)	Monoclonal Antibody/Antibodies
MOE	margin of error
NIAID	(United States) National Institute of Allergy and Infectious Diseases
NIH	(United States) National Institutes of Health
OHRP	Office of Human Research Protections
PP	per-protocol
PRO	(DAIDS) Protocol Registration Office
RSC	(DAIDS) Regulatory Support Center
SAE(s)	Serious Adverse Event(s)
SAP	Statistical Analysis Plan
SDMC	Statistical and Data Management Center
SARS	Severe Acute Respiratory Syndrome
SARS-CoV-2	Severe Acute Respiratory Syndrome Coronavirus 2
sIRB	single IRB
SOE	Schedule of Events
SSP	Study-Specific Procedures manual
TLS	Time-location Sampling
US	United States

## CoVPN 5002

### SARS-COV-2 PREVALENCE STUDY

#### SCHEMA

**Design:**

Cross-sectional surveys of (1) adults residing in senior living facilities and attending outpatient healthcare facilities, and (2) the general population in each selected research site community.

**Population:**

- 1) Adults residing in senior living facilities (nursing homes, assisted or independent living facilities) and attending outpatient healthcare facilities in neighborhoods of selected research sites
- 2) Adults and children (> 2 months of age) in neighborhoods of selected research sites

**Study Size:**

For each research site, up to 3,920 individuals will be enrolled from one, two, or all three of the following populations (must include at least community venues):

- 1) senior living facilities (nursing homes, assisted or independent living facilities; n = 500)
- 2) outpatient healthcare facilities (n = 500)
- 3) community venues distributed across four age categories (0-17, 18-39, 40-59, 60+ years) (n = 730 per stratum or 2920)

Total sample size = 3,920 x up to 20 clinical research sites

**Study Duration:**

Approximately sixteen (16) months for overall project. Two (2) months for protocol development and institutional review board (IRB) approval, followed by:

- 1) Facility-based surveys: 12 months (3 months for site preparation and initiation, 3 months for enrollment/sample collection, 4 months for shipping and laboratory testing\*, 2 months for close-out), concurrent with
- 2) Time-location sampling (TLS) surveys: 14 months (3 months for site preparation and initiation, 6 months for enrollment/sample collection, 6 months for shipping and laboratory testing\*, 2 months for close-out)

\*Some activities will be concurrent with enrollment

**Study Location:**

Catchment areas surrounding US-based Clinical Research Sites (CRSs) of the: HIV Prevention Trials Network (HPTN), HIV Vaccine Trials Network (HVTN), Infectious Diseases Clinical Research Consortium (IDCRC), International Maternal Pediatric Adolescent AIDS Clinical Trials Group (IMPAACT), and the AIDS Clinical Trials Group (ACTG); to be specified in the Site Announcement Memo

**Study Methods:**

Blood collection for SARS-CoV-2 antibody testing and characterization of the serologic response to SARS-CoV-2 infection; nasal mid-turbinate swab collection for SARS-CoV-2 RNA testing; collection of saliva in a subset of participants to evaluate the performance of diagnostic SARS-CoV-2 assays using these matrices; administration of tablet-based survey. Medical records abstraction for senior living facility participants who are unable to respond to the study survey.

**Primary Objective:**

To estimate the prevalence of SARS-CoV-2 IgG seropositivity among individuals in communities surrounding selected NIAID clinical research sites

**Secondary Objectives:**

- 1) To estimate prevalence of SARS-CoV-2 infection based on results of SARS-CoV-2 RNA testing
- 2) To estimate prevalence of SARS-CoV-2 infection by presence versus absence of symptoms consistent with COVID-19
- 3) To estimate seroprevalence of SARS-CoV-2 among:
  - a. Those without past or current symptoms consistent with COVID-19
  - b. Those with no prior positive SARS-CoV-2 testing, but who report close contact with confirmed or presumed cases
  - c. Those with history of co-morbid medical conditions
- 4) To assess association between demographic, clinical and social factors with SARS-CoV-2 infection and seroprevalence
- 5) To estimate potential size of populations for referral to COVID-19 prevention and treatment studies
- 6) To assess knowledge, attitudes, and behavior about SARS-CoV-2 and COVID-19
- 7) To assess performance characteristics of PCR-based and serologic SARS-CoV-2 tests using saliva samples

**Exploratory Objectives:**

- 1) To model epidemiologic impact over time of COVID-19 in the study communities, including modeled incidence and prevalence of COVID-19.
- 2) To conduct laboratory testing in a subset of participants to characterize SARS-CoV-2 viruses and the host response to SARS-CoV-2 infection; this may include testing for SARS-CoV-2 IgM antibodies. This testing may also include phylogenetic analysis of SARS-CoV-2 and co-infections with other viruses, including viruses that impact the specificity of SARS-CoV-2 serologic assays.

## 1.0 INTRODUCTION

### 1.1 Background and Rationale

Currently, the United States (US) has far more confirmed COVID-19 cases than any other country. The US epidemic is remarkably heterogeneous, with many cities and communities experiencing a disproportionately high disease burden and mortality. For example, at present, Minneapolis, Houston, Atlanta, and Durham NC, are projected to bear the brunt of the US epidemic and in the future, other communities may see an increase in the number of COVID-19 cases.

There is an urgent need to address the COVID-19 pandemic in a multipronged, expeditious manner to identify effective interventions for COVID-19 treatment and prevention. The National Institute of Allergy and Infectious Diseases (NIAID) has therefore mobilized its major research networks under the banner of the COVID-19 Prevention Network (CoVPN) to work together in the rapid evaluation of COVID-19 treatment and prevention strategies. This approach leverages the well-established infrastructure, expertise, and on-going partnership of these networks with the resources of the NIH and developers of vaccines, monoclonal antibodies, drugs, and other potential interventions for COVID-19 treatment and prevention. It also leverages the multidisciplinary expertise of investigators and staff in the networks, including clinical trial design and implementation, laboratory, and statistical expertise. In addition, the networks have research sites that allow for rapid enrollment of participants at traditional and non-traditional venues in the US and globally. The engagement of research sites from multiple NIH networks, including the HPTN, HVTN, ACTG and IMPAACT and the Infectious Diseases Clinical Research Consortium (IDCRC), will accelerate recruitment, diversify the trial cohorts, and build capacity for the conduct of future COVID-19 treatment and prevention studies. In this protocol, the terms “clinical research site (CRS)” and “research site” and “site” refer to clinical research sites from selected NIAID networks and “community” refers to the geographic area surrounding each CRS.

The COVID-19 pandemic is evolving, with diverse and dynamic impacts in different regions and populations in the US. Over the coming months and years, it is likely that different communities will experience the epidemic to varying extents, with resurgence in other communities. The beginning of the US epidemic was marked by an outbreak at a nursing home near Seattle, Washington (1) and nursing homes in many other states have had similarly tragic experiences with extremely high incidence and mortality rates (2). The nursing home outbreaks reflect the observation, now noted in multiple settings (2), that COVID-19 is more likely to present as a severe infection among those over the age of 65 and those with medical co-morbidities (3) and mortality rates are approximately ten times higher for these groups, even among those not living in a skilled nursing facility. These morbidity and mortality patterns among older individuals with medical conditions underscore the importance of treatment and prevention interventions tailored to this population. Accurate and detailed estimates of SARS-CoV-2 seroprevalence and COVID-19 in a rigorously sampled and geographically broad population will inform the development of these interventions.

The epidemic has also been marked by harsh disparities in COVID-19 rates and other health outcomes among African American and Latino communities who have substantially higher attack rates and higher mortality compared with any other racial or ethnic group (4) across the US. The communities surrounding several NIAID CRSs have suffered from not only longstanding racial inequalities, but also socioeconomic disparities in housing and employment, as well as varied access to health and other essential services. These populations also have a high prevalence of co-morbidities associated with higher incidence of COVID-19 (5-8), more severe manifestations of COVID-19 disease (9-11), higher mortality from COVID-19 (11), and have poorer health outcomes from a variety of illnesses overall (12). As with the observations among the elderly, these racial and ethnic factors all compel the need

for the systematic collection of COVID-19-related data from populations at high risk for and highly impacted by COVID-19 and from the general population in their communities to enable the successful design and conduct of COVID-19 targeted prevention and treatment studies and provision of access to these populations of promising prevention and treatment interventions.

The proposed research will provide comprehensive information on communities impacted by COVID-19 beyond surveillance studies currently in the field (see Appendix IV for summary of existing studies). It will directly contribute to preparedness for SARS-CoV-2 vaccine and other COVID-19 prevention studies by determining the prevalence of SARS-CoV-2 infection and seroprevalence among samples of individuals of different ages who are recruited from communities where NIAID CRSs are situated. All prevalence estimates will be weighted for study design, non-response and post-stratification population projections in order to generate estimates that are representative of the NIAID CRS communities. This research will determine the extent to which children and adults in these areas have SARS-CoV-2 infection or evidence of prior SARS-CoV-2 infection (based on results of antibody tests, self-report, and medical records). Additionally, data captured through questionnaires about participants' household members with COVID-like illness and deaths, combined with serologic data from participants, may also provide information about transmission dynamics within households. Questionnaire data will inform estimates of the percent of individuals of different age groups, including children, who may have had an asymptomatic COVID-19 infection. The frequency of infection among children and whether infected children play an important role in community transmission is poorly understood (13). The study will also provide estimates of the association of SARS-CoV-2 seroprevalence with medical co-morbidities that have been associated with more severe disease outcomes and will also identify demographic and social risk factors associated with infection (10). Finally, this research will provide important information about SARS-CoV-2 transmission, COVID-19 disease, attitudes about and uptake of containment and mitigation measures, racial and ethnic health disparities, varied access to testing and public health resources by key demographic indicators, prospects for new prevention and treatment strategies, and be used to inform mathematical models of disease progression and projection of future COVID-19 risk.

Other SARS-CoV-2 studies that are ongoing in the US use different sampling approaches and/or assess different populations (see Appendix IV). For example, the NIH's ongoing "SARS-CoV-2 Pandemic Serosurvey and Blood Sampling," (NCT04334954) will estimate the number of adults over the age of 18 years with SARS-CoV-2 antibody among those who have not had confirmed COVID-19 or known exposure to COVID-19. The study uses non-probability sampling to assemble a cohort of 15,000 adults from three locations (Bethesda MD, Birmingham AL and Pittsburgh PA). The ongoing study has a longitudinal component as participants can re-enroll up to four times if more than 30 days have elapsed since their last enrollment.

In contrast, the current study uses time-location sampling to assess cohorts that are representative of the communities near NIAID research sites across the US; includes young children and adolescents as well as adults; includes a detailed assessment of older adults with medical co-morbidities, including those residing in skilled nursing facilities; estimates the number and proportion with active infection as well as both symptomatic and asymptomatic prior infection; and will provide a more detailed picture of the racial and ethnic profile of the COVID epidemic in the US.

In summary, this study will provide critically important information on the prevalence of current and prior SARS-CoV-2 infections in communities in the US where NIAID research sites are situated. It will assess the impact of COVID-19 on the communities, model the potential impact of different prevention interventions, and set the foundation for COVID-19 prevention and treatment trials in these communities. It will also provide critical information to guide site selection and the allocation of numbers of participants for future prevention and treatment studies and will provide valuable samples for key laboratory assessments related to SARS-CoV-2 infection and the COVID-19 epidemic.

## 1.2 Study Design

Sites will be selected from existing NIAID CRSs. For most metropolitan areas, one CRS will be selected with consideration given to the population they serve. For larger metropolitan areas (e.g., New York, Chicago, Los Angeles), two or more CRSs may be selected to gain full representation of the region. Adjustments may be made to the selected CRSs as the dynamics of the pandemic shift.

The study will begin with community consultations with existing site community advisory boards and key stakeholders, including relevant experts from local health departments, local healthcare and social service providers, and caregivers for elderly and chronically ill populations. These consultations will help identify specific venues, key community attributes, appropriate social venues, and times and days when venues are likely to be well populated. The consultations will also include discussions about how best to report results of SARS-CoV-2 RNA testing, to local health departments, as required by health regulations. Advice will be sought from the community advisory boards to help develop communication and social mobilization plans that ensure high participation rates.

The study is observational in design with a single study visit. Recruitment, enrollment, and data collection will take place using two strategies: facility-based surveys of senior living facilities and time-location sampling (TLS) surveys of outpatient clinics and community venues. Facility-based surveys will begin with each research site creating a list of nearby senior living facilities that are interested in participating in the study. A census of all participating senior living facilities will be conducted to recruit up to 500 individuals per research site. Consent will be obtained from legal guardians for participants who are not able to provide consent. Medical abstraction will be performed for these participants in lieu of administering the study questionnaire.

Adults attending outpatient medical clinics and members of the general population attending community venues will be recruited through TLS. TLS is a well-established study methodology that uses ethnographically-informed mapping of social spaces to create a “clinic-time-day universe” or “venue-time-day universe” of commercial establishments, social service providers, schools, places of worship, parks, and transit hubs from which a given population can be systematically approached and surveyed (14). The approach is appropriate to reach a representative sample of individuals participating in social activities and interactions in the study communities.

Adults who were recruited at a selected clinic or venue, have the capacity for consent and are willing and able to answer a brief survey and provide a blood sample and nasal mid-turbinate swab, will be included in the study. Children aged 2 months - 17 years will be included, with the consent of their parent or legal guardian and their assent from youth 7 – 17 years of age; the parent/guardian will complete the questionnaire for those under age 10 years and will assist those ages 11-15. These inclusion criteria allow for sampling of all populations impacted by the COVID-19 pandemic, including residents with chronic diseases such as obesity, hypertension, and diabetes, which have been shown to increase severity and mortality in COVID-19 patients. Data collection from parents/guardians about their children is also critical for understanding the prevalence of COVID-19 in younger patients, to understand the role children of different ages may play in household and community transmission dynamics and to learn about factors that may put some children at increased risk.

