### 2.2 Secondary Objectives and Endpoints

Secondary Objectives	Secondary Endpoints
1) To estimate prevalence of SARS-CoV-2 infection based on results of SARS-CoV-2 RNA testing	Proportion of individuals with SARS-CoV-2 infection (based on SARS-CoV-2 RNA testing)
2) To estimate prevalence of SARS-CoV-2 infection by presence versus absence of symptoms consistent with COVID-19	Proportion of individuals with SARS-CoV-2 infection (based on SARS-CoV-2 RNA testing) who report lack of symptoms versus presence of symptoms consistent with COVID-19
3) To estimate seroprevalence of SARS-CoV-2 among: 
 
a) Those without past or current symptoms consistent with COVID-19,
 
b) Those with no prior positive SARS-CoV-2 testing, but who report close contact with confirmed or presumed cases, and
 
c) Those with history of co-morbid medical conditions
 
	Proportion of individuals with SARS-CoV-2 IgG antibodies who report: 
 
a) Prior confirmed or presumed COVID-19 vs. those who report never having symptoms,
 
b) No prior COVID-19 but who report close contact with a COVID-19 case (as defined by the US Centers for Disease Control and Prevention), and
 
c) Co-morbid medical conditions such as obesity, hypertension and diabetes
 

Secondary Objectives	Secondary Endpoints
4) To assess association between demographic, clinical and social factors with SARS-CoV-2 infection and seroprevalence	Socioeconomic, demographic and clinical correlates of COVID-19 and/or SARS-CoV-2 seroprevalence with particular interest in racial and ethnic health disparities
5) To estimate potential size of populations for referral to COVID-19 prevention and treatment studies	Extrapolated population sizes of 
 
a) Those with active COVID-19,
 
b) Those who have serologic evidence of recent and/or past SARS-CoV-2 infection, and
 
c) Those who have negative RNA and serologic SARS-CoV-2 tests
 

6) To assess knowledge, attitudes, and behavior about SARS-CoV-2 and COVID-19	Knowledge and attitudes about SARS-CoV-2 and COVID-19, and uptake of public health interventions including shelter in place orders, social distancing, and mask use

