### **3.2 Exclusion Criteria**

**3.2.1** Previous enrollment in this study, either from the same or another CRS community.

**3.2.2** Any condition that, in the opinion of the study staff, would make participation in the study unsafe, complicate interpretation of study outcome data, or otherwise interfere with achieving the study objectives.

Note – COVID-19 vaccination is not exclusionary

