#### **4.7 SARS-CoV-2 Counseling**

All study participants will receive counseling messages consistent with the US Center for Disease Control and Prevention (CDC) and local public health authorities. These messages will include instructions on use of masks and how to isolate from others, duration of isolation, how to monitor for worsening of symptoms, and how to connect to social services as needed.

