### **6.0 STATISTICAL CONSIDERATIONS**

#### **6.1 Review of Study Design**

This is a cross-sectional study of individuals residing within the vicinity of selected research sites in the United States who are (i) residing in senior living facilities, (ii) visiting outpatient clinics at given times; and (iii) members of the general population who attend any of the listed community venues at given times. The study aims to estimate prevalence of SARS-CoV-2 infection and IgG seropositivity separately in each of these populations (sampling strategies described above). Given that the three primary endpoints and their respective samples are independent, sites may recruit from one, two, or all three population groups, depending on site capacity (sites must enroll from at least the community venues). Consenting and assenting participants who satisfy the inclusion and exclusion criteria described in Section 3.0, will answer a brief survey and provide a blood sample and nasal mid-turbinate swab(s).

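### Community-venue RNA results (secondary objectives 1, 2 and 5a) describe people who attend venues, but the protocol claims them for, and extrapolates them to, whole communities

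*Protocol*

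**What the plan says.** **Who can be sampled.** Section 6.1 defines the community population as "members of the general population who attend any of the listed community venues at given times". Section 3.3.1 draws venue time blocks and then individuals within them. Section 1.2 describes the reach of the method in the same limited way: "The approach is appropriate to reach a representative sample of individuals participating in social activities and interactions in the study communities".

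**What is claimed.** Section 1.1 says all prevalence estimates will be weighted "in order to generate estimates that are representative of the NIAID CRS communities". It also lists the number and share of people with active infection among the study's outputs. Section 6.3 describes the age-group estimates, for infection as well as IgG, as being among community residents.

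**Which endpoints are involved.** In Section 2.2, objective 1 is RNA prevalence. Objective 2 divides RNA-positive people into those "who report lack of symptoms versus presence of symptoms consistent with COVID-19". Endpoint 5a is an extrapolated population size for "Those with active COVID-19". Section 6.3.2 obtains objective 5 from design-based survey estimates.

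**How the sample is weighted.** Section 6.3 uses base weights from the sample design, a nonresponse adjustment, and raking and post-stratification to county census figures. The variables it names are age, sex, race/ethnicity, education and income.

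**The concern.** For the RNA endpoints, being out at a venue is not independent of the outcome. Someone who is ill, or who knows of a positive test, is plausibly less likely to be at a shop, park or transit hub during the infection. The protocol shows that this behaviour is expected: Section 4.7 gives participants "instructions on use of masks and how to isolate from others, duration of isolation", and Section 4.8 adds isolation counselling for those who test positive.

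Expanding such a sample to residents would understate current infection. If symptomatic people are the ones who stay away, it would also overstate the asymptomatic share. Objective 5 is meant to size populations for referral to prevention and treatment studies, and Section 1.1 says the results will guide site selection and participant allocation. The cases missed matter for those uses.

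**Working it through.** **1. The plan's own figures.** Section 6.2 gives 730 per age stratum at prevalence 5%, margin 2.5% and design effect 2.5:

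n = 2.5 × 1.96² × 0.05 × 0.95 / 0.025² = 729.9, so 730 reproduces.

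4 × 730 = 2,920, and 2,920 + 500 + 500 = 3,920. The venue sample is therefore the largest component, and Section 3.3 makes it the only mandatory one. None of this arithmetic is in dispute, and selection bias does not shrink as n grows.

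**2. Selection model.** Let P be true RNA prevalence, a the true asymptomatic share of RNA-positives, and r the venue attendance of symptomatic infected people relative to everyone else. The documents give none of these three values.

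- Captured fraction of infections: f = a + (1 − a)r
- Observed prevalence: P·f / (P·f + 1 − P)
- Observed asymptomatic share: a / f

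For any r < 1, f is below 1. Observed prevalence then falls and the asymptomatic share rises.

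**3. Illustrations at an assumed P = 1%.**

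| a | r | f | observed / true prevalence | observed asymptomatic share |
|---|---|---|---|---|
| 0.50 | 0.50 | 0.75 | 0.75 | 67% |
| 0.50 | 0.10 | 0.55 | 0.55 | 91% |
| 0.40 | 0.75 | 0.85 | 0.85 | 47% |
| 0.40 | 0.50 | 0.70 | 0.70 | 57% |
| 0.40 | 0.25 | 0.55 | 0.55 | 73% |
| 0.20 | 0.50 | 0.60 | 0.60 | 33% |
| 0.60 | 0.50 | 0.80 | 0.80 | 75% |

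First row in full: f = 0.5 + 0.5 × 0.5 = 0.75. Observed prevalence = 0.0075 / (0.0075 + 0.99) = 0.75%. Share = 0.5 / 0.75 = 67%.

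**4. If diagnosed asymptomatic people also stay away.** Suppose their relative attendance is 0.8, with a = 0.5 and r = 0.5. Then f = 0.5 × 0.8 + 0.5 × 0.5 = 0.65 and the asymptomatic share is 0.40 / 0.65 = 62%. Prevalence falls further and the share is distorted less. The share is biased upward only if symptomatic people are absent more often than asymptomatic ones.

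**5. Weighting.** If r < 1 holds within a cell of age, sex, race/ethnicity, education and income, rescaling that cell to its census total leaves its infected fraction unchanged. The bias passes through to the weighted estimate.

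**6. Clinics.** Ill people may attend because they are ill, so r may exceed 1. At a = 0.40 and r = 2, f = 0.4 + 0.6 × 2 = 1.6 and the observed share is 0.4 / 1.6 = 25%, below the true 40%. The documents do not settle the sign.

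**7. Against sampling error.** At one site with n = 2,920, P = 1% and design effect 2.5, the 95% half-width is 1.96 × √(2.5 × 0.01 × 0.99 / 2,920) = 0.57 percentage points. The bias in the first row is 1.00 − 0.75 = 0.25 points. At a single site it would sit inside the interval. A bias with the same sign at every site does not average out over the planned 20 or so sites.

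**The case against.** The best defence is that the protocol already limits itself. Sections 1.2 and 6.1 describe attendees, and Section 6.3 calls the clinic group attending patients. Each population is analysed separately. The weighting variables are introduced as examples, and a sensitivity analysis could sit in the analysis plan. Much of this stands: Section 1.2 is the accurate sentence and is not the error. But the frame, the representativeness claim, the community-resident label and the extrapolated endpoint are all fixed in the protocol. A later weighting specification of the kind described cannot recover people whom the frame misses because they are infected. Deferred visits at the research site (Section 4.0) do not help, since recruitment still happens at the venue.

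Several stronger readings are tempting, and the documents do not support them:

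- **That the study's own counselling removes cases.** It comes at or after enrolment, and Section 3.2 bars re-enrolment. It is evidence of expected behaviour, not a cause of the loss.
- **That clinics share the venue bias.** The sign is open there.
- **That all RNA results are affected.** Senior living residents are recruited where they live (Sections 1.2 and 3.3.3).
- **That the discretionary exclusion adds a second loss.** Section 3.2 allows exclusion for "Any condition that, in the opinion of the study staff, would make participation in the study unsafe, complicate interpretation of study outcome data". However, the pre-screening described in Section 4.1.1 has no symptom question, staff wear full protective equipment (Section 3.0), and the study plans for positive participants. Nothing says ill people are turned away.
- **That the size is known.** The percentages above are assumptions.

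**Conclusion.** The point holds for the community-venue sample. Sections 1.1, 2.2 (endpoint 5a), 6.3 and 6.3.2 carry an attendee sample over to community residents for an outcome that plausibly affects attendance, and the named weights cannot undo that.

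The direction is conditional. If symptomatic infected people attend less than others, RNA prevalence and 5a are too low; if they also attend less than asymptomatic infected people, the asymptomatic share is too high. Relative attendance of one half with an even symptom split gives the 75% and 67% shown above, as illustration only. The model holds attendance otherwise equal. It does not address whether habitual venue-goers differ in exposure, which is one reason to call 5a a likely bound and not a certain one.

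Only secondary objectives are affected. IgG seropositivity is much less exposed, because recovered people can be back at venues. The change is worth making but is not critical.

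**What to change.** - In Sections 2.2 and 6.3, define the venue- and clinic-based RNA estimates, and the objective 2 symptom split, as applying to attendees. Align the representativeness wording in Section 1.1 and the community-resident label in Section 6.3.
- Report the community-venue part of 5a as a likely lower bound, with a sensitivity range over relative attendance r. Do not apply attendee RNA prevalence to all residents.
- Show the already planned IgG result by symptom history (endpoint 3a) beside the objective 2 split. It describes past infection, so it gives context and does not replace objective 2.

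No change to the exclusion criteria is needed on this ground. Household-reported illness should not be added to the RNA count: it mixes case definitions, may double count, and Section 4.3 does not establish that it captures current cases.

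The cost is wording plus one sensitivity calculation, with no new data. The downside is that 5a becomes a bound or range, which is less attractive as a headline figure.
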